**Table 4      Eligibility for safety analyses**

Event	N used for deriving % per subject for Vaccination phase	N used for deriving % per dose for Vaccination phase
Solicited general symptom	All subjects with at least one solicited general symptom documented as either present or absent (i.e., symptom screen completed)	All study visits with study vaccine administered and with at least one solicited general symptom documented as either present or absent (i.e., symptom screen completed)
Solicited local symptom	All subjects with at least one solicited local symptom documented as either present or absent (i.e., symptom screen completed)	All study visits with study vaccine administered and with at least one solicited local symptom documented as either present or absent (i.e., symptom screen completed)
Unsolicited symptom	All subjects with study vaccine administered	All study visits with study vaccine administered

The intensity of the following solicited AEs will be assessed as described:

**Table 5 Intensity scales for solicited symptoms**

Adverse Event	Intensity grade	Parameter
Pain at injection site	0	None
	1	Mild: Any pain neither interfering with nor preventing normal everyday activities.
	2	Moderate: Painful when limb is moved and interferes with everyday activities.
	3	Severe: Significant pain at rest. Prevents normal everyday activities.
Redness at injection site		Record greatest surface diameter in mm
Swelling at injection site		Record greatest surface diameter in mm
Fever*		Record temperature in °C/F
Headache	0	Normal
	1	Mild: Headache that is easily tolerated
	2	Moderate: Headache that interferes with normal activity
	3	Severe: Headache that prevents normal activity
Fatigue	0	Normal
	1	Mild: Fatigue that is easily tolerated
	2	Moderate: Fatigue that interferes with normal activity
	3	Severe: Fatigue that prevents normal activity
Gastrointestinal symptoms (nausea, vomiting, diarrhea and/or abdominal pain)	0	Normal
	1	Mild: Gastrointestinal symptoms that are easily tolerated
	2	Moderate: Gastrointestinal symptoms that interfere with normal activity
	3	Severe: Gastrointestinal symptoms that prevent normal activity
Arthralgia	0	Normal
	1	Easily tolerated
	2	Interferes with normal activity
	3	That prevents normal activity
Myalgia	0	Normal
	1	Easily tolerated
	2	Interferes with normal activity
	3	That prevents normal activity
Shivering	0	Normal
	1	Easily tolerated
	2	Interferes with normal activity
	3	That prevents normal activity

\*Fever is defined as temperature  $\geq 38.0^{\circ}\text{C} / 100.4^{\circ}\text{F}$ . The preferred location for measuring temperature in this study will be the oral cavity.

The maximum intensity of local injection site redness/swelling/fever will be graded at GSK Biologicals as follows:

**Table 6 Grading for redness/swelling**

	Redness/swelling
0:	$\leq 20 \text{ mm}$
1:	$> 20 - \leq 50 \text{ mm}$
2:	$> 50 - \leq 100 \text{ mm}$
3:	$> 100 \text{ mm}$

The grading for temperature will be the following:

- Grade 1: 38 – 38.5°C
- Grade 2: >38.5 – 39°C
- Grade 3: > 39.0°C

Laboratory parameters will be graded according to the FDA toxicity grading scale for hematology/biochemistry parameters.

**Table 7 FDA toxicity grading scales for hematology/biochemistry parameters**

Serum*	Mild (Grade 1)	Moderate (Grade 2)	Severe (Grade 3)	Potentially Life Threatening (Grade 4)**
Blood Urea Nitrogen - BUN	23 – 26	27 – 31	> 31	Requires dialysis
Creatinine – mg/dL	1.5 – 1.7	1.8 – 2.0	2.1 – 2.5	> 2.5 or requires dialysis
Liver Function Tests –ALT, AST increase by factor	1.1 – 2.5 x ULN	2.6 – 5.0 x ULN	5.1 – 10 x ULN	> 10 x ULN

ULN = upper limit of the normal range.

\*The laboratory values provided in the tables serve as guidelines and are dependent upon institutional normal parameters. Institutional normal reference ranges should be provided to demonstrate that they are appropriate.

\*\*The clinical signs or symptoms associated with laboratory abnormalities might result in characterization of the laboratory abnormalities as Potentially Life Threatening (Grade 4). For example, a low sodium value that falls within a Grade 3 parameter (125-129 mE/L) should be recorded as a Grade 4 hyponatremia event if the subject had a new seizure associated with the low sodium value.

Hematology*	Mild (Grade 1)	Moderate (Grade 2)	Severe (Grade 3)	Potentially Life Threatening (Grade 4)
Hemoglobin (Female) - gm/dL	11.0 – 12.0	9.5 – 10.9	8.0 – 9.4	< 8.0
Hemoglobin (Female) change from baseline value - gm/dL	Any decrease – 1.5	1.6 – 2.0	2.1 – 5.0	> 5.0
Hemoglobin (Male) - gm/dL	12.5 – 13.5	10.5 – 12.4	8.5 – 10.4	< 8.5
Hemoglobin (Male) change from baseline value - gm/dL	Any decrease – 1.5	1.6 – 2.0	2.1 – 5.0	> 5.0
WBC Increase - cell/mm 	10 800 – 15 000	15 001 – 20 000	20 001 – 25 000	> 25 000
WBC Decrease - cell/mm 	2 500 – 3 500	1 500 – 2 499	1 000 – 1 499	< 1 000
Lymphocytes Decrease - cell/mm 	750 – 1 000	500 – 749	250 – 499	< 250
Neutrophils Decrease - cell/mm 	1 500 – 2 000	1 000 – 1 499	500 – 999	< 500
Eosinophils - cell/mm 	650 – 1 500	1 501 – 5 000	> 5 000	Hyper-eosinophilic
Platelets Decreased - cell/mm 	125 000 – 140 000	100 000 – 124 000	25 000 – 99 000	< 25 000

\*The laboratory values provided in the tables serve as guidelines and are dependent upon institutional normal parameters. Institutional normal reference ranges should be provided to demonstrate that they are appropriate

**12.2.6. Number of decimals displayed**

The following decimal description from the decision rules will be used for the demography, immunogenicity and safety/reactogenicity.

**Table 8 Number of decimals**

Display Table	Parameters	Number of decimal digits
Demographic characteristics	Age (y)	Min, Max: 0 Mean, percentiles, SD: 1
Demographic characteristics	Weight (kg), height (cm), BMI,	Min, Max: 1 Mean, percentiles, SD: 2
Immunogenicity	GMT/C, including LL & UL of CI	1
Immunogenicity	Ratio of GMT/C	2
Reactogenicity	Duration of symptoms (days)	Min, Max: 0 Mean, percentiles, SD: 1
All summaries	% of count, including LL & UL of CI	1
All summaries	% of difference, including LL & UL of CI	2

## 13. ANNEX 2: STUDY SPECIFIC MOCK TFL

The following standard and study specific mocks tables and figures will be used.

The data display, title and footnote presented are for illustration purposes and will be adapted to the study specificity as indicated in the TFL TOC. Note that there may be few changes between the study specific SAP mock TFL and the final TFLs as editorial/minor changes do not require an SAP amendment.

### Template 1 Number of subjects by country and center <cohort name>

		<Each group> N=XXXX		<Each group> N=XXXX		Total N=XXXX	
Country	Center	n	%	n	%	n	%
<each country>	<each center>	XXX	XX.X	XXX	XX.X	XXX	XX.X
	All	XXX	XX.X	XXX	XX.X	XXX	XX.X

Short group label = long group label

N = total number of subjects

n = number of subjects in a given center or country

% = (n/N) x 100

### Template 2 Number of enrolled subjects by country <cohort name>

		<Each group> N=XXXX		<Each group> N=XXXX		Total N=XXXX	
Country		n	%	n	%	n	%
<each country>		XXX	XX.X	XXX	XX.X	XXX	XX.X
		XXX	XX.X	XXX	XX.X	XXX	XX.X

Short group label = long group label

Screening Failure: Subjects for whom all eligibility criteria were not fulfilled at the time of screening conclusion

Not Assigned: Subjects withdrawn/lost to follow up before screening conclusion or Visit 1 and subjects who completed the screening period after randomization closure

N = total number of subjects

n = number of subjects in a given center or country

% = (n/N) x 100

Note: Screening Failure and Not Assigned are displayed only for enrolled set.

**Template 3 Number of subjects enrolled in the study and number of subjects excluded from the Per-Protocol set for analysis of immunogenicity <at Day 85 analysis / Month 14+28 days analysis / Final analysis>**

	Total			<Each group>		<Each group>	
	n	s	%	n	s	n	s
Title							
Enrolled set							
Invalid informed consent or fraudulent data (900)							
Study vaccine dose not administered but subject number allocated (1030)							
Exposed set							
Administration of vaccine(s) forbidden in the protocol (1040)							
Randomization code broken at the investigator site or GSK safety department (1060)							
Study vaccine dose not administered according to protocol (1070)							
Vaccine temperature deviation (1080)							
Expired vaccine administered (1090)							
Protocol violation (inclusion/exclusion criteria) (2010)							
Unknown baseline anti H1-stalk antibody titer by ELISA (2020)							
Administration of any medication forbidden by the protocol (2040)							
Intercurrent medical condition (2060)							
Non-compliance with vaccination schedule (including wrong and unknown vaccination dates) (2080)							
Non-compliance with blood sampling schedule (including wrong and unknown dates) (2090)							
Essential serological data missing (2100)							
Obvious incoherence or abnormality or error in data (2120)							
Per Protocol set							

Short group label = long group label

Screening Failure: Subjects for whom all eligibility criteria were not fulfilled at the time of screening conclusion

Not Assigned: Subjects withdrawn/lost to follow up before screening conclusion or Visit 1 and subjects who completed the screening period after randomization closure

Note: Subjects may have more than one elimination code assigned

n = number of subjects with the elimination code assigned excluding subjects who have been assigned a lower elimination code number

s = number of subjects with the elimination code assigned

% = percentage of subjects in the considered PP set relative to the Exposed set

**Template 4 Number and percentage of subjects in the Per-Protocol set for analysis of immunogenicity over time**

Visit description	<Each group>			<Each group>			Total		
	N	n	%	N	n	%	N	n	%
VISIT 1 (D1)									
VISIT 2 (D7)									

Short group label = long group label

N = number of subjects with a valid sample at the specified visit

n = number of subjects in the Per Protocol set for analysis of immunogenicity among subjects with a valid sample at the specified visit

% = percentage of subjects in the Per Protocol set for analysis of immunogenicity relative to the number of subjects with a valid sample at the specified visit

Visit 2, Visit 5 and Visit 9 only concern the CMI sub-cohort subjects

**Template 5 Number of subjects vaccinated, completed and withdrawn with reason for withdrawal <at Day 85 analysis / Month 14+28 days analysis / Final analysis> <Cohort name>**

		<Each Group> N=XXXX	< Each Group> N=XXXX	Total N=XXXX
Number of subjects vaccinated		XXX	XXX	XXX
End of study status [Each category]		XXX	XXX	XXX
Reasons for withdrawal: [Reasons]		XXX	XXX	XXX

Short group label = long group label

N = total number of subjects

n/% = number / percentage of subjects in a given category

Vaccinated = number of subjects who were vaccinated in the study

Completed = number of subjects who completed last study visit

Withdrawn = number of subjects who did not come for the last visit

Unknown = number of subjects who have not come for the last visit yet

**Template 6 List of (S)AEs leading to study/treatment discontinuation <Cohort name>**

Group	Subject ID	Country	Gender	Race	Preferred Term	SAE	Causality	Outcome	Type of discontinuation*

\*Type of discontinuation refers to whether the discontinuation is a treatment discontinuation or study follow-up discontinuation

**Template 7 Visit attendance <Cohort name>**

		<Each group> N=XXXX		<Each group> N=XXXX		Total N=XXXX	
Visit	Attendance	n	%	n	%	n	%
<each visit>	Attended	XXX	XX.X	XXX	XX.X	XXX	XX.X
	Not attended yet	XXX	XX.X	XXX	XX.X	XXX	XX.X
	Withdrawal at visit or at a preceding visit	XXX	XX.X	XXX	XX.X	XXX	XX.X
	Not attended	XXX	XX.X	XXX	XX.X	XXX	XX.X

Short group label = long group label

N = Number of subjects in each group or in total

n/% = number / percentage of subjects in a given category

**Template 8 Minimum and maximum activity dates <Cohort name>**

Visit Description	Parameter	<each group>		Overall
		Date	Date	
<each visit>	Minimum	DDMMYYYY	DDMMYYYY	DDMMYYYY
	Maximum	DDMMYYYY	DDMMYYYY	DDMMYYYY

Short group label = long group label

## Template 9 Summary of demographic characteristics <Cohort name>

	<Each group> N=XXXX		<Each group> N=XXXX		Total N=XXXX	
	Value or n	%	Value or n	%	Value or n	%
Age in years at screening/visit 1						
N with data	XXX		XXX		XXX	
Mean	XXX.X		XXX.X		XXX.X	
SD	XXX.X		XXX.X		XXX.X	
Median	XXX.X		XXX.X		XXX.X	
Minimum	XXX		XXX		XXX	
Maximum	XXX		XXX		XXX	
Age category						
18-30 years	XXX	XX.X	XXX	XX.X	XXX	XX.X
31-39 years	XXX	XX.X	XXX	XX.X	XXX	XX.X
Height (cm)						
N with data	XXX		XXX		XXX	
Mean	XXX.X		XXX.X		XXX.X	
SD	XXX.X		XXX.X		XXX.X	
Median	XXX.X		XXX.X		XXX.X	
Minimum	XXX		XXX		XXX	
Maximum	XXX		XXX		XXX	
Weight (kg)						
N with data	XXX		XXX		XXX	
Mean	XXX.XX		XXX.XX		XXX.XX	
SD	XXX.XX		XXX.XX		XXX.XX	
Median	XXX.XX		XXX.XX		XXX.XX	
Minimum	XXX.X		XXX.X		XXX.X	
Maximum	XXX.X		XXX.X		XXX.X	
BMI (kg/m^2)						
N with data	XXX		XXX		XXX	
Mean	XXX.XX		XXX.XX		XXX.XX	
SD	XXX.XX		XXX.XX		XXX.XX	
Median	XXX.XX		XXX.XX		XXX.XX	
Minimum	XXX.X		XXX.X		XXX.X	
Maximum	XXX.X		XXX.X		XXX.X	
Gender						
Male	XXX	XX.X	XXX	XX.X	XXX	XX.X
Female	XXX	XX.X	XXX	XX.X	XXX	XX.X
Ethnicity						
<Each ethnicity>	XXX	XX.X	XXX	XX.X	XXX	XX.X
...	XXX	XX.X	XXX	XX.X	XXX	XX.X
Geographic Ancestry						
<Each geographic ancestry>	XXX	XX.X	XXX	XX.X	XXX	XX.X
...	XXX	XX.X	XXX	XX.X	XXX	XX.X
Study phase						
Phase I	XXX	XX.X	XXX	XX.X	XXX	XX.X
Phase II	XXX	XX.X	XXX	XX.X	XXX	XX.X
CMI sub-cohort						
Yes	XXX	XX.X	XXX	XX.X	XXX	XX.X
No	XXX	XX.X	XXX	XX.X	XXX	XX.X

Short group label = long group label

N = total number of subjects

n/% = number / percentage of subjects in a given category

Value = value of the considered parameter

N with data = number of subjects with documentation of the corresponding data

SD = standard deviation

Note: for enrolled set add footnotes:

Screening Failure: Subjects for whom all eligibility criteria were not fulfilled at the time of screening conclusion

Not Assigned: Subjects withdrawn/lost to follow up before screening conclusion or Visit 1 and subjects who completed the screening period after randomization closure

**Template 10 History of seasonal influenza vaccination in the previous 3 seasons before study vaccination <Cohort name>**

		< Each Group> N=XXXX		< Each Group> N=XXXX		Total N=XXXX	
Characteristics	Categories	n	%	n	%	n	%
At least one season	Yes	xxx	xx.x	xxx	xx.x	xxx	xx.x
	No						
	Unknown	xxx	xx.x	xxx	xx.x	xxx	xx.x
Season 2014-2015	Yes	xxx	xx.x	xxx	xx.x	xxx	xx.x
	No						
	Unknown	xxx	xx.x	xxx	xx.x	xxx	xx.x
Season 2015-2016	Yes	xxx	xx.x	xxx	xx.x	xxx	xx.x
	No						
	Unknown	xxx	xx.x	xxx	xx.x	xxx	xx.x
Season 2016-2017	Yes	xxx	xx.x	xxx	xx.x	xxx	xx.x
	No						
	Unknown	xxx	xx.x	xxx	xx.x	xxx	xx.x

Short group label = long group label

N = total number of subjects

n = number of subjects with influenza vaccination during the specified season

% = n / Number of subjects with available results x 100

**Template 11 Medical History <Cohort name>**

		<Each group> N=XXXX		<Each group> N=XXXX		Total N=XXXX	
SOC		n	%	n	%	n	%
<each SOC>		XXX	XX.X	XXX	XX.X	XXX	XX.X
		XXX	XX.X	XXX	XX.X	XXX	XX.X
		XXX	XX.X	XXX	XX.X	XXX	XX.X

Short group label = long group label

N = total number of subjects

n = number of subjects in a given category

% = (n/N) x 100

**Template 12 Study population <Cohort name>**

	<Each group> N=XXXX	<Each group> N=XXXX	Total N=XXXX
Number of subjects			
Planned, N	xxx	xxx	xxx
Randomized, N <cohort name>	xxx	xxx	xxx
Completed, n (%)	xxx (xx.x)	xxx (xx.x)	xxx (xx.x)
<Unknown>	xxx	xxx	xxx
Demographics			
N <cohort name>	xxx	xxx	xxx
Females: Males	xxx:xxx	xxx:xxx	xxx:xxx
Mean Age, <unit> (SD)	xxx.x (xxx.x)	xxx.x (xxx.x)	xxx.x (xxx.x)
Median Age, <unit> (minimum, maximum)	xxx (xxx,xxx)	xxx (xxx,xxx)	xxx (xxx,xxx)
<MOST FREQUENT CATEGORY OF RACE>	xxx (xx.x)	xxx (xx.x)	xxx (xx.x)
<SECOND MOST FREQUENT CATEGORY OF RACE>	xxx (xx.x)	xxx (xx.x)	xxx (xx.x)
<THIRD MOST FREQUENT CATEGORY OF RACE>	xxx (xx.x)	xxx (xx.x)	xxx (xx.x)

Short group label = long group label

N = Total number of subjects

n = number of subjects during the specified period

% = n / Number of subjects x 100

SD = standard deviation

**Template 13 Exposure to study vaccines <cohort name>**

	<Each group> N=XXXX		<Each group> N=XXXX		Total N=XXXX	
	N	%	n	%	n	%
Number of subjects receiving						
Exactly 1 Dose	Xx	xx.x	xx	xx.x	xx	xx.x
Exactly 2 Doses	Xx	xx.x	xx	xx.x	xx	xx.x
...	xx	xx.x	xx	xx.x	xx	xx.x
At least 1 Dose	xx	xx.x	xx	xx.x	xx	xx.x
Total number of doses administered during the study	xx		xx		xx	

Short group label = long group label

N = number of subjects in each group or in total included in the considered cohort

n = number of subjects/doses in the given category

% = percentage of subjects in the given category

**Template 14 Compliance in completing solicited symptoms information <Cohort name>**

DOSE	Symptom information	<Each group>		<Each group>		
		N	n	Compliance (%)	N	n
DOSE <each dose number>	General SS	xxx	xxx	xx.x	xxx	xxx
	Local SS	xxx	xxx	xx.x	xxx	xxx
TOTAL	General SS	xxx	xxx	xx.x	xxx	xxx
	Local SS	xxx	xxx	xx.x	xxx	xxx

Short group label = long group label

N = Number of administered doses

n = number of doses with SS returned

General SS = Symptom screens used for the collection of general solicited AEs

Local SS = Symptom screens used for the collection of local solicited AEs

Compliance (%) = (n / N) X 100

**Template 15 Incidence and nature of <grade 3> adverse events (solicited and unsolicited) <with causal relationship to vaccination> reported during the 7-day (Days 1-7) post-vaccination period following each dose and overall <Cohort name>**

		<Each group>					<Each group>				
					95% CI					95% CI	
Dose	Symptoms	N	n	%	LL	UL	N	n	%	LL	UL
DOSE 1	Any symptom	XXX	XXX	XX.X	XX.X	XX.X	XXX	XXX	XX.X	XX.X	XX.X
	General symptoms	XXX	XXX	XX.X	XX.X	XX.X	XXX	XXX	XX.X	XX.X	XX.X
	Local symptoms	XXX	XXX	XX.X	XX.X	XX.X	XXX	XXX	XX.X	XX.X	XX.X
DOSE 2	Any symptom	XXX	XXX	XX.X	XX.X	XX.X	XXX	XXX	XX.X	XX.X	XX.X
	General symptoms	XXX	XXX	XX.X	XX.X	XX.X	XXX	XXX	XX.X	XX.X	XX.X
	Local symptoms	XXX	XXX	XX.X	XX.X	XX.X	XXX	XXX	XX.X	XX.X	XX.X
OVERALL/DOSE	Any symptom	XXX	XXX	XX.X	XX.X	XX.X	XXX	XXX	XX.X	XX.X	XX.X
SUBJECT	General symptoms	XXX	XXX	XX.X	XX.X	XX.X	XXX	XXX	XX.X	XX.X	XX.X
	Local symptoms	XXX	XXX	XX.X	XX.X	XX.X	XXX	XXX	XX.X	XX.X	XX.X

Short group label = long group label

For each dose:

N = number of subjects with the corresponding administered dose

n/% = number/percentage of subjects presenting at least one type of symptom following the corresponding dose

For overall/dose:

N = number of administered dose

n/% = number/percentage of doses followed by at least one type of symptom

For overall/subject:

N = number of subjects with at least one administered dose

n/% = number/percentage of subjects presenting at least one type of symptom

95% CI = Exact 95% confidence interval; LL = lower limit, UL = upper limit

**Template 16 Incidence of solicited local symptoms reported during the 7-day  
(Days 1-7) post-vaccination period following each dose and overall  
<Cohort name>**

Dose	Symptom	Type	<Each Group>			
			95% CI			
N	n	%	LL	UL		
DOSE x	<Each local symptom>	ALL GRADE $\geq 2$ GRADE 3 MEDICAL ADVICE ALL GRADE $\geq 2$ GRADE 3 MEDICAL ADVICE				
OVERALL/DOSE	<Each local symptom>	ALL GRADE $\geq 2$ GRADE 3 MEDICAL ADVICE ALL GRADE $\geq 2$ GRADE 3 MEDICAL ADVICE				
OVERALL/SUBJECT	<Each local symptom>	ALL GRADE $\geq 2$ GRADE 3 MEDICAL ADVICE ALL GRADE $\geq 2$ GRADE 3 MEDICAL ADVICE				

Short group label = long group label

For each dose:

N = number of subjects with the corresponding documented dose

n/% = number/percentage of subjects reporting the type of symptom at least once

For Overall/dose:

N = number of documented doses

n/% = number/percentage of doses followed by at least one type of symptom

For overall/subject:

N = number of subjects with at least one documented dose

n/% = number/percentage of subjects reporting the type of symptom at least once

95% CI = Exact 95% confidence interval; LL = lower limit, UL = upper limit

**Template 17 Incidence of solicited general symptoms reported during the 7-day (Days 1-7) post-vaccination period following each dose and overall <Cohort name>**

Dose	Symptom	Type	<Each Group>				
			95% CI				
N	n	%	LL	UL			
DOSE x	<Each general symptom including Temperature>	ALL					
		GRADE $\geq$ 2					
		GRADE 3					
		RELATED					
		GRADE $\geq$ 2 RELATED					
		GRADE 3 RELATED					
		MEDICAL ADVICE					
	Temperature (C)	ALL					
		$\geq$ 38.0					
		>38.5					
		>39.0					
		>39.5					
		>40.0					
		RELATED					
		$\geq$ 38.0 RELATED					
		>38.5 RELATED					
		>39.0 RELATED					
		>39.5 RELATED					
		>40.0 RELATED					
		MEDICAL ADVICE					
OVERALL/DOSE	<Each general symptom including Temperature>	ALL					
		GRADE $\geq$ 2					
		GRADE 3					
		RELATED					
		GRADE $\geq$ 2 RELATED					
		GRADE 3 RELATED					
		MEDICAL ADVICE					
	Temperature (C)	ALL					
		$\geq$ 38.0					
		>38.5					
		>39.0					
		>39.5					
		>40.0					
		RELATED					
		$\geq$ 38.0 RELATED					
		>38.5 RELATED					
		>39.0 RELATED					
		>39.5 RELATED					
		>40.0 RELATED					
		MEDICAL ADVICE					
OVERALL/SUBJECT	<Each general symptom including Temperature>	ALL					
		GRADE $\geq$ 2					
		GRADE 3					
		RELATED					
		GRADE $\geq$ 2 RELATED					
		GRADE 3 RELATED					
		MEDICAL ADVICE					

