- **Enrolment:** the study will follow a staggered enrolment with 2 steps; the first being Phase I (N = ~80) and the second being Phase II (N = ~390):
  - Phase I: During the Phase I enrolment, subjects will be vaccinated one at a time, at least 60 minutes apart, with a maximum of 10 subjects/day until ~80 subjects are enrolled (i.e. to obtain treatment groups of at least 8 subjects/group). If no safety issue is identified by the Independent Data Monitoring Committee (IDMC) upon review of the 7-day post-dose 1 safety data (Days 1-7) of all Phase I subjects (N = ~80), Phase II enrolment will be allowed to start.
  - Phase II: Subjects will be enrolled and vaccinated without limitation on the number of vaccinees per day or time between consecutive subjects.
- **Vaccination schedule:**
  - Two primary doses at Visit 1 (Day 1) and Visit 4 (Day 57).
  - A booster dose at Visit 8 (Month 14).
- **Definition of the different epochs:**
  - Epoch 001: Screening (Day -28 to -2) – only for Phase I subjects.
  - Epoch 002: Primary starting at Visit 1 (Day 1) and ending at Visit 7 (Month 8).
  - Epoch 003: Booster starting at Visit 8 (Month 14) and ending at Visit 12 (Month 26).

- **Intervals between study visits**

Interval	Optimal length of interval	Allowed interval**
Screening to Visit 1*	2-28 days	
Visit 1 → Visit 2	7 days	7-9 days
Visit 1 → Visit 3	28 days	28-38 days
Visit 1 → Visit 4	56 days	56-66 days
Visit 4 → Visit 5	7 days	7-9 days
Visit 4 → Visit 6	28 days	28-38 days
Visit 4 → Visit 7	168 days	168-196 days
Visit 4 → Visit 8	336 days	336-364 days
Visit 8 → Visit 9	7 days	7-9 days
Visit 8 → Visit 10	28 days	28-38 days
Visit 8 → Visit 11	168 days	168-196 days
Visit 8 → Visit 12	336 days	336-364 days

\* Only applicable for Phase I subjects. Screening evaluations may be completed 2 to 28 days before Day 1. Site staff should allow sufficient time between the screening and Day 1 visits to receive and review screening safety laboratory test results. If a delay occurs such that the interval between screening and the Day 1 vaccination exceeds 28 days, a re-screening visit should be scheduled before Visit 1.

\*\* Visits out of the allowed interval can lead to elimination from the Per-Protocol set for immunogenicity analysis.

- **Sampling schedule:**

- Blood samples for safety assessment will be drawn from all subjects at all visits: Screening\*, Days 1, 8, 29, 57, 64, 85, Month 8, Month 14, Month 14 + 7 days, Month 14 + 28 days, Month 20 and Month 26.

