### **6.3. Analysis of safety**

The analysis will be performed on the ES.

All analyses will be descriptive. Data will be presented by dose, overall/dose and overall/subject. Outputs will be presented by study group. Analyses will be repeated pooling groups according to the adjuvant (AS01, AS03, no adjuvant).

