## 12. ANNEX 1 STANDARD DATA DERIVATION RULE AND STATISTICAL METHODS

### 12.1. Statistical Method References

The exact two-sided 95% CIs for a proportion within a group will be the Clopper-Pearson exact CI [Clopper CJ, Pearson ES. The use of confidence or fiducial limits illustrated in the case of binomial. *Biometrika*. 1934; 26: 404-413].

The standardized asymptotic two-sided 95% CI for the group difference in proportions is based on the method described in the following paper: Robert G. Newcombe, interval estimation for the difference between independent proportions: comparison of eleven methods, *Statist Med*. 1998; 17, 873-890]. The standardized asymptotic method used is the method six.

The 95% CIs of the group GMT ratios will be computed using an ANCOVA model on the logarithm10 transformation of the titers. The ANCOVA model will include the vaccine group as fixed effects and the logarithm10 transformation of titers at Day 1. For the evaluation of adjuvant of preferred priming sequence, the vaccine group will be replaced by 2 fixed effects: the adjuvant type (AS01, AS03, No adjuvant) and the number of priming doses (1 priming dose with cH8/1N1, 1 priming dose with cH5/1N1, 2 priming doses with cH8/1N1 and cH5/1N1).

The 95% CI for GMTs will be obtained within each group separately. The 95% CI for the mean of log-transformed titer will be first obtained assuming that log-transformed values were normally distributed with unknown variance. The 95% CI for the GMTs will then be obtained by exponential-transformation of the 95% CI for the mean of log-transformed titer.

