## CONFIDENTIAL

207543 (FLU D-SUIV-ADJ-001)  
Statistical Analysis Plan Amendment 3

Dose	Symptom	Type	<Each Group>			95% CI	
			N	n	%	LL	UL
	Temperature (C)	ALL					
		$\geq 38.0$					
		$>38.5$					
		$>39.0$					
		$>39.5$					
		$>40.0$					
		RELATED					
		$\geq 38.0$ RELATED					
		$>38.5$ RELATED					
		$>39.0$ RELATED					
		$>39.5$ RELATED					
		$>40.0$ RELATED					
		MEDICAL ADVICE					

Short group label = long group label

For each dose:

N = number of subjects with the corresponding documented dose

n/% = number/percentage of subjects reporting the type of symptom at least once

For Overall/dose:

N = number of documented doses

n/% = number/percentage of doses followed by at least one type of symptom

For overall/subject:

N = number of subjects with at least one documented dose

n/% = number/percentage of subjects reporting the type of symptom at least once

95% CI = Exact 95% confidence interval; LL = lower limit, UL = upper limit

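### In the overall/dose safety rows, exact 95% intervals treat up to three doses from one subject as independent, so the stated 95% level is not guaranteed

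*SAP*

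**What the plan says.** Section 6.3 of the current SAP (Amendment 3) plans three levels of safety summary: "Data will be presented by dose, overall/dose and overall/subject". Section 12.1 fixes the interval: "The exact two-sided 95% CIs for a proportion within a group will be the Clopper-Pearson exact CI".

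In Annex 2, the overall/dose block of Template 15 defines the denominator as "N = number of administered dose" and the numerator as "n/% = number/percentage of doses followed by at least one type of symptom". Templates 16 and 17 use the same numerator over "N = number of documented doses". Template 24 does likewise for concomitant medication, counting doses after which a medication was started. In each of these templates a single footnote covers all row types: "95% CI = Exact 95% confidence interval; LL = lower limit, UL = upper limit".

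Section 2 schedules doses at Day 1, Day 57 and Month 14 for 47 subjects per group. Seven of the ten groups receive PBS at Day 57. Section 6.3 also repeats the safety analyses with groups pooled by adjuvant. The SAP contains no design effect, robust variance or other allowance for repeated doses, and no caveat that the overall/dose interval ignores them.

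**The concern.** A Clopper-Pearson interval holds its level when the count is binomial: independent trials with one probability. An overall/dose count meets neither condition. Someone who reacts to one dose is more likely to react to the next, which makes the count more variable than binomial and the interval too short. Mixing PBS and vaccine doses with different rates reduces the variance relative to a binomial with the average rate, which works the other way.

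At stake is the meaning of the 95% label on these rows. The net error depends on the symptom and on how many doses in a group are PBS, so columns read side by side may carry different real confidence under the same label.

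**Working it through.** **Inputs.** From the SAP: 47 subjects per group and up to 3 doses each (section 2), so up to 47 x 3 = 141 doses per group; Clopper-Pearson at 95% (section 12.1). Assumed, because the SAP gives no figures: the within-subject correlation rho and the dose-specific symptom rates.

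**Step 1: reproduce the stated level.** With 141 independent doses and a common rate p, coverage is at least 95.2% and averages 96.1% over p = 0.05 to 0.95. The 95% label holds under independence.

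**Step 2: equal rates, correlated doses.** With exchangeable correlation the variance of the dose count is 141 p(1-p)(1+2 rho), so the design effect is 1+2 rho. Coverage was computed exactly by enumerating a beta-binomial count over 47 subjects.

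| rho | 1+2 rho | coverage, p=0.3 | coverage, p=0.5 | mean, p=0.05-0.95 |
|---|---|---|---|---|
| 0 | 1.0 | 95.7% | 95.7% | 96.1% |
| 0.05 | 1.1 | 94.7% | 94.6% | 95.1% |
| 0.1 | 1.2 | 93.6% | 93.5% | 94.1% |
| 0.2 | 1.4 | 91.3% | 91.3% | 92.0% |
| 0.3 | 1.6 | 89.0% | 89.0% | 89.8% |
| 0.5 | 2.0 | 84.7% | 84.7% | 85.6% |

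More subjects do not help. Under the same equal-rate model, an adjuvant pool of 3 x 47 = 141 subjects with three doses each, at p = 0.5, covers 93.8%, 89.4% and 85.1% at rho 0.1, 0.3 and 0.5. With only two doses counted per subject (47 subjects, p = 0.5), the figures are 93.9%, 91.5% and 89.1%.

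**Step 3: what it does to one interval.** For 71 of 141 doses the planned interval is 41.8-58.9%. At rho 0.3 the effective sample size is 141/1.6 = 88.1, and Clopper-Pearson on that size gives 39.5-61.2%. The width goes from 17.1 to 21.7 points.

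**Step 4: rare events.** By simulation at p = 1%, coverage is 97-98% for rho 0.05-0.15 and 96% at rho 0.3; at p = 2% it is 96-97% for rho 0.05-0.15. By p = 5% the protection is fading: 95.2%, 93.5% and 91.7% at rho 0.1, 0.2 and 0.3 (exact enumeration).

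**Step 5: PBS counted as a dose.** If doses are independent with rates p1, p2, p3 and mean pm, the variance relative to binomial is [sum of pi(1-pi)] / [3 pm(1-pm)].

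- Assumed rates 0.90/0.15/0.90: (0.09 + 0.1275 + 0.09)/(3 x 0.65 x 0.35) = 0.3075/0.6825 = 0.45. A probit random intercept with latent correlation up to 0.7 raises this to 0.65. Coverage is 99.2-99.8%, which is too wide.
- Assumed rates 0.80/0.15/0.80: 0.4475/0.7292 = 0.61 under independence. Coverage is about 96-99% across the correlations tried.
- Assumed rates 0.50/0.25/0.50: 0.6875/0.7292 = 0.94 under independence, coverage 96.5%. With latent correlation 0.3, 0.5 and 0.7 the ratio is 1.29, 1.53 and 1.79, and coverage is 92.9%, 90.3% and 87.4%, which is too narrow.

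A latent correlation is larger than the correlation between the yes/no outcomes. At equal rates of 0.4, latent 0.3 gives a variance ratio of 1.38, so rho = 0.38/2 = 0.19.

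**The case against.** The strongest reply is that little depends on these rows. Section 4.1 defines the reactogenicity endpoint after each vaccine dose. That is the per-dose row, with one observation per subject, where Clopper-Pearson is valid; the same is true of the overall/subject row. Section 6.3 makes all safety analyses descriptive, and the only interval-based decision rule in section 7 concerns ELISA titre ratios. All of this stands. A reader might infer that the intervals on the primary endpoint are wrong, or that groups cannot be compared on reactogenicity. The documents do not support either inference, since valid per-dose and per-subject rows are planned for that purpose.

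A second reply is that sections 6.3.1 and 6.3.2 attach exact intervals to percentages of subjects, while the interval on doses comes from mock-table footnotes that section 13 calls illustrative. This softens the point. But section 6.3 itself plans the overall/dose presentation, and the SAP offers no other interval for it.

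Third, the size is assumed. That also stands: at rho 0.05 average coverage is still 95.1%, and very rare rows, such as the highest fever thresholds may prove to be, stay at or above nominal unless rho is high. It would be wrong to say that every overall/dose interval misses its level.

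Fourth, one might infer that groups given PBS always have intervals that are too wide. Step 5 shows that this needs a strong contrast between vaccine and PBS; a mild contrast with correlation gives the opposite. Table 4 in section 12.2.5 counts visits with study vaccine administered and does not settle whether PBS visits are included.

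**Conclusion.** The point holds as a limited defect of method. The overall/dose rows of Templates 15, 16, 17 and 24 carry an interval labelled exact whose 95% level is guaranteed only under independence and a common rate, and the design provides neither. For common symptoms (30-50%) with equal rates per dose, real coverage is about 94%, 91%, 89% and 85% at assumed rho of 0.1, 0.2, 0.3 and 0.5. The shortfall largely disappears at rho of about 0.05 or below and for very rare events. Where PBS doses are counted, the error can go either way. These figures rest on assumed correlations and rates; the SAP fixes only the number of subjects, the number of doses and the method. No primary-endpoint row and no decision rule is affected. It should be corrected because the label is not earned and the correction is cheap.

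**What to change.** In the overall/dose rows of Templates 15, 16, 17 and 24, print n and % without a confidence interval. Template 20 already does this for combined solicited and unsolicited AEs. It works on every row, including those with no events.

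If an interval is kept, add a sentence to section 12.1 specifying one that accounts for clustering by subject. Two options are Clopper-Pearson on an effective sample size divided by the design effect, or, for common events, GEE with robust variance. With rho known, the design-effect version gives coverage of 95.4-97.0% for rho 0.1-0.5 and p = 0.1-0.7; in practice rho must be estimated. State a fallback for rows with zero, very few or all events. With zero events a logit GEE is undefined and a subject-level bootstrap collapses to a point. In simulation at p = 1%, the GEE was undefined in 26-35% of samples and the percentile bootstrap covered only 66-74%, against 96-98% for Clopper-Pearson.

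Keep Clopper-Pearson for the per-dose and overall/subject rows. The cost is one fewer interval, or somewhat wider intervals for most common symptoms, in a descriptive row. Data collection and sample size do not change.
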